Table 9-2	Follow Up Requirements for Liver Events and Laboratory Triggers ...	51

List of figures

Figure 1-1	Co-ordinated effects of FXR on metabolism	16
Figure 1-2	Effect of LJN452 in the chronic treatment rat ANIT model	17
Figure 3-1	Study design schematic	22

List of abbreviations

AE	adverse event
ALP	alkaline phosphatase
ALT	alanine aminotransferase
ANCOVA	analysis of covariance
AST	aspartate aminotransferase
b.i.d.	twice a day
BA	bile acid
BMI	Body Mass Index
BSEP	bile salt export pump
BUN	blood urea nitrogen
CD-ROM	compact disc – read only memory
CFR	Code of Federal Regulation
CK	creatinine kinase
CRF	Case Report/Record Form (paper or electronic)
CRO	Contract Research Organization
CV	coefficient of variation
EC	Ethics committee
EC50	half maximal effective concentration
ECG	Electrocardiogram
EDC	Electronic Data Capture
ELISA	Enzyme-linked immunosorbent assay
FDA	Food and Drug Administration
FXR	Farnesoid X-receptor
GCP	Good Clinical Practice
GGT	Gamma-glutamyl transferase
GLP	Good Laboratory Practice
h	Hour
HIV	human immunodeficiency virus
i.v.	Intravenous
ICH	International Conference on Harmonization of Technical Requirements for Registration of Pharmaceuticals for Human Use

IEC	Independent Ethics Committee
IRB	Institutional Review Board
IRT	Interactive Response Technology
LDH	lactate dehydrogenase
LLN	lower limit of normal
LLQ	lower limit of quantification
mg	milligram(s)
ml	milliliter(s)
o.d.	once a day
OECD	Organization for Economic Co-operation and Development
p.o.	Oral
PA	Posteroanterior
pBAD	primary bile acid diarrhea
PD	pharmacodynamic(s)
PK	pharmacokinetic(s)
RBC	red blood cell(s)
REB	Research Ethics Board
s.c.	Subcutaneous
SAE	serious adverse event
SD	standard deviation
SeHCAT	Selenium Homocholic Acid Taurine
SGOT	serum glutamic oxaloacetic transaminase
SGPT	serum glutamic pyruvic transaminase
SHP	Small Heterodimer Partner
TBL	total bilirubin
ULN	upper limit of normal
ULQ	upper limit of quantification
WBC	white blood cell(s)

Pharmacokinetic definitions and symbols

AUC _{tau}	The area under the plasma (or serum or blood) concentration-time curve from time zero to the end of the dosing interval tau [mass x time / volume]
AUC _{tau,ss}	The area under the plasma (or serum or blood) concentration-time curve from time zero to the end of the dosing interval tau at steady state [mass x time / volume]
C _{av,ss}	The average steady state plasma (or serum or blood) concentration during multiple dosing
CL/F	The apparent systemic (or total body) clearance from plasma (or serum or blood) following extravascular administration [volume / time]
C _{max}	The observed maximum plasma (or serum or blood) concentration following drug administration [mass / volume]
C _{max,ss}	The observed maximum plasma (or serum or blood) concentration following drug administration at steady state [mass / volume]
C _{min,ss}	The lowest plasma (or serum or blood) concentration observed during a dosing interval at steady state [mass / volume]
R _{acc}	The accumulation ratio
T _{max}	The time to reach the maximum concentration after drug administration [time]

Corporate Confidential Information

Corporate Confidential Information

Protocol synopsis

Protocol number	CLJN452X2202
Title	A double blind, randomized placebo controlled crossover multiple dose study of LJN452 to assess safety, tolerability and efficacy in patients with primary bile acid diarrhea (pBAD).
Brief title	To assess safety and tolerability and establish efficacy of LJN452 in patients with primary bile acid diarrhea.
Sponsor and Clinical Phase	Novartis. Phase 2
Intervention type	Drug.
Study type	Interventional.
Purpose and rationale	To assess safety, tolerability and efficacy of LJN452 in patients with pBAD.
Primary Objective(s)	
 • To determine the safety and tolerability of LJN452 in patients with pBAD. • To assess the effect of LJN452 on clinical symptoms experienced by patients with pBAD.
Secondary Objectives	
 • To assess the pharmacokinetics of LJN452 in pBAD patients. • Assess the effect of LJN452 on use of rescue medications during the study period.
Study design	This is a multi-center, double blind (patient and investigator blind, sponsor open label), randomized placebo controlled, crossover study to assess safety, tolerability and efficacy of LJN452 in patients with primary bile acid diarrhea (pBAD).
Population	The study population will be comprised of patients with primary bile acid diarrhea. Approximately 30 patients will be enrolled in the study and randomized, with at least 24 patients expected to complete the study.
Inclusion criteria	
 • A history of diarrheal symptoms for at least 3 months prior to dosing - Average stool frequency of at least 3 per day when off therapy AND Average stool form of >5 on Bristol Stool Chart. • Previous laboratory or radiological confirmation of bile acid malabsorption within the last 5 years with either fecal bile acid loss of $\geq 2,000 \mu\text{mol}$ per 48 hours OR 7 day $^{75}\text{Selenium}$ homocholic acid taurine ($^{75}\text{SeHCAT}$) retention. • Age ≥ 18 years.
Exclusion criteria	
 • Patients with other diagnoses leading to diarrhea, including colorectal neoplasia, ulcerative colitis, Crohn's disease, celiac disease, chronic pancreatitis, drug-induced diarrhea or active infection AND Patients who have not been investigated by standard clinical assessments to exclude these disorders. • Treatment with bile acid sequestrants (colestyramine, colestipol,

[figure not shown]
	
colesevelam) for 2 weeks before the first dose of LJN452. A washout of 14 days for these agents will be allowed before first dosing.
 
 • History of extrahepatic biliary obstructive disease or complete biliary obstruction. • Women of child-bearing potential, defined as all women physiologically capable of becoming pregnant, unless they are using highly effective methods of contraception • A positive Hepatitis B surface antigen or Hepatitis C test result. • History of immunodeficiency diseases, including a positive HIV (ELISA and Western blot) test result.
Investigational and reference therapy	
 • Single oral dose of LJN452 60 µg daily for 14 days. • Single oral dose of placebo to LJN452 0 µg daily for 14 days.
Efficacy/PD assessments	
 • Change from baseline in stool frequency and stool form per Bristol Stool Chart.
Safety assessments	
 • Safety endpoints include type and frequency of adverse events, serious adverse events, and laboratory, vital signs, physical, and ECG abnormalities.
Other assessments	
 • PK. • Use of rescue medication. • Markers of target engagement.
Data analysis	
A repeated measures analysis will be done for the two-dimensional endpoint: weekly stool frequency and the corresponding average stool form. The analysis will include fixed effects for sequence (Drug/Placebo or Placebo/Drug), Treatment (Week 1 Drug, Week 2 Drug, Week 1 Placebo, Week 2 Placebo), and period (1 or 2). The model will assume an arbitrary 2 by 2 covariance matrix for the two-dimensional endpoint (frequency, form) and a compound symmetry covariance matrix for each individual endpoint. Point estimates of the treatment effect on weekly & biweekly stool frequency and the corresponding average stool form will be reported together with 95% simultaneous confidence intervals (confidence ellipsoids).

Key words	Primary bile acid diarrhea, FXR agonist, bile acid malabsorption.

1 Introduction

1.1 Background

LJN452 is a highly potent agonist of the bile acid receptor Farnesoid X Receptor (FXR), which is expressed in liver, intestine and kidney. In the liver, FXR agonism increases expression of genes involved in canalicular and basolateral bile acid efflux and bile acid detoxifying enzymes while inhibiting basolateral bile acid uptake by hepatocytes and inhibiting bile acid synthesis ([Calkin and Tontonoz 2012](#)). FXR activation represses bile acid synthesis in the liver through induction of Small Heterodimer Partner (SHP), which is a negative regulator of Cyp7a1, the rate-limiting enzyme of the neutral bile acid biosynthetic pathway ([Goodwin et al 2000](#)). Furthermore, FXR agonists increase excretion of bile acids through the kidney, increase bile acid binding proteins in the ileum and stimulate FGF15/FGF19 expression (a key regulator of bile acid metabolism). Thus, FXR acts as a sensor of elevated bile acids and initiates homeostatic responses to control bile acid levels, a feedback mechanism that is believed to be impaired in bile acid malabsorption ([Pattni et al 2012, Walters 2014](#)).

Figure 1-1 Co-ordinated effects of FXR on metabolism

FXR regulates bile acid metabolism through multiple mechanisms in the liver and intestine. The processes regulated by FXR are shown in rectangular boxes. Genes are shown with up or down arrows to indicate the direction of regulation by FXR agonists. Arrows are used to show the flow of bile acids in the enterohepatic circulation or the movement of FGF15 (rodents) or FGF19 (human) from the enterocyte to the hepatocyte. In normal physiology, FXR detects increased levels of bile acids and responds by decreasing bile acid synthesis and bile acid uptake while increasing bile acid modification and secretion in the liver. In the intestine, FXR detects increased bile acid levels and decreases bile acid absorption and increases secretion of FGF15 or FGF19. The net result is a decrease in the overall levels of bile acids. Adapted from [Calkin and Tontonoz 2012](#).

1.1.1 Relevant data summary

The most relevant data for the present study are summarized in the sections below. For detailed information, please refer to the Investigator's Brochure.

Corporate Confidential Information

1.2 Study purpose

The purpose of this study is to determine whether LJN452 improves the symptoms of bile acid diarrhea and to assess its safety and tolerability profile in patients with primary bile acid diarrhea (pBAD) to guide decision-making regarding further clinical development in this indication.

2 Study objectives

2.1 Primary objective(s)

Primary objective(s)	Endpoints related to primary objective(s)

• To determine the safety and tolerability of LJN452 in patients with primary bile acid diarrhea.• To assess the effect of LJN452 on clinical symptoms experienced by patients with primary bile acid diarrhea.	
• Safety endpoints include type and frequency of adverse events, serious adverse events, and laboratory, vital signs, physical, and ECG abnormalities.• Changes from baseline in stool frequency and in stool form per Bristol Stool Chart.

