11.4 Analysis of the primary variable(s)

11.4.1 Variable(s)

The primary analysis variables are: a) stool frequency, b) and stool form assessed by the Bristol stool chart.

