11.4.2 Statistical model, hypothesis, and method of analysis

A repeated measures analysis will be done for the two-dimensional endpoint: weekly stool frequency and the corresponding average stool form. The analysis will include fixed effects for sequence (Drug/Placebo or Placebo/Drug), Treatment (Week 1 Drug, Week 2 Drug, Week 1 Placebo or Week 2 Placebo), and period (1 or 2). The model will assume an arbitrary 2 by 2 covariance matrix for the two-dimensional endpoint (frequency, form) and a compound symmetry covariance matrix for each individual endpoint. Point estimates of the weekly & biweekly treatment effect on stool frequency and form will be reported together with 95% simultaneous confidence intervals (confidence ellipsoids).

Baseline weekly stool frequency and the corresponding average stool form will be analyzed similarly using the method described above to assess unequal carryover effects.

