6.1.2 Descriptive analyses

Summary statistics (including median and IQR) of the stool frequency and average stool form (weekly and biweekly) for each treatment as well as the difference and % change between the 2 treatments will be provided by visit. Baseline data will be summarized by treatment and visit. The number and percentage of patients with each stool form will be provided by treatment and visit. The stool frequency and stool form data will be listed by treatment sequence, patient and visit.

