6.1.3 Statistical model, assumptions and hypotheses

A repeated measures analysis will be done for the two-dimensional endpoint: weekly stool frequency and the corresponding average stool form. The analysis will include fixed effects for sequence (Drug/Placebo or Placebo/Drug), Treatment (Week 1 drug, Week 2 drug, Week 1 placebo or Week 2 Placebo), and period (1 or 2). The model will assume an arbitrary 2 by 2 covariance matrix for the two-dimensional endpoint (frequency, form) and a compound symmetry covariance matrix for each individual end point. Point estimates of the weekly & biweekly treatment effect on stool frequency and the corresponding average stool form will be reported together with 95% simultaneous confidence intervals (confidence ellipsoids).

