6.1.3.3 Supportive analysis

Baseline weekly stool frequency and the corresponding average stool form will be analyzed using the same method as described in Section 6.1.3 to assess unequal carryover effects.

The number and percentage of subjects using loperamide will be tabulated by treatment. Total weekly loperamide use (in mg) will be summarized by treatment and visit (including baseline). The stool index, calculated as [weekly stool frequency*mean stool form]+loperamide use [weekly mg*3], will also be summarized and analyzed using a linear mixed effects model including sequence, period and treatment as fixed effects and subject nested within sequence as a random effect.

Corporate Confidential Information

7 Statistical methods for safety and tolerability data

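### Does the change-from-baseline wording of the stool endpoint, with no diary week defined as baseline, undermine the planned efficacy analysis?

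*Protocol*

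**What the plan says.** Protocol 2.1 gives the efficacy endpoint as "Changes from baseline in stool frequency and in stool form per Bristol Stool Chart", and the synopsis has nearly the same words: "Change from baseline in stool frequency and stool form per Bristol Stool Chart".

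The analysis sections are worded differently. Protocol 11.4.1, repeated in SAP 6.1.1, states: "The primary analysis variables are: a) stool frequency, b) and stool form assessed by the Bristol stool chart". The model in protocol 11.4.2 and SAP 6.1.3 takes the weekly values as the response. Its fixed effects are sequence, a four-level treatment-by-week factor and period. Baseline does not enter.

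Baseline appears in three supporting outputs:

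- The carryover check. Protocol 11.4.2: "Baseline weekly stool frequency and the corresponding average stool form will be analyzed similarly using the method described above to assess unequal carryover effects". SAP 6.1.3.3: "Baseline weekly stool frequency and the corresponding average stool form will be analyzed using the same method as described in Section 6.1.3".
- The stool summaries. SAP 6.1.2: "Baseline data will be summarized by treatment and visit".
- The loperamide summaries. SAP 6.1.3.3: "Total weekly loperamide use (in mg) will be summarized by treatment and visit (including baseline").

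There are two explicit baseline rules. Protocol 3.1 treats the Day 1 pre-dose assessment as baseline. Protocol 11.5.2 and SAP 7.1.2, for laboratory data only, take the latest value obtained after washout and ahead of dosing in each period. Protocol 3.1 sets a run-in of 7 or 14 days and a washout of 7 to 28 days.

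**The concern.** Read literally, the stated endpoint is never analysed. Section 2.1 promises a change from baseline, the model uses on-treatment values, and SAP 6.1.2 summarises differences between treatments and baseline data separately. A reader could fear that the estimate reported is not the one promised.

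The second worry is the undefined week. A Day 1 pre-dose visit is a time point, so it cannot itself be a weekly count. A 14-day run-in or a 28-day washout contains more than one possible week, and no minimum number of completed diary days is given. The carryover check borrows a model whose treatment factor is split by week, while the shortest run-in and washout hold one week each. The sponsor's trial team is unblinded throughout (protocol 6.5), so an unwritten choice could in principle be made with treatment codes in view. At stake would be the reading of the carryover check and of the baseline tables.

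**Working it through.** The plan gives no figure to reproduce here; the sample size section is blacked out. The check is algebra on the planned contrasts and a comparison of the passages.

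**1. Drug-placebo contrast with one common baseline.** For a patient with both periods, let W_D and W_P be the weekly values on drug and placebo, and B a single pre-study baseline.

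(W_D − B) − (W_P − B) = W_D − W_P

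The baseline cancels. With complete data, the endpoint as worded and the variable as modelled give the same treatment difference.

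**2. The same contrast with a baseline for each period.** Assume variance σ² and equal correlation ρ among the two baseline weeks and four treatment weeks. The plan assumes compound symmetry for each endpoint; extending it to the baseline weeks is my assumption.

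- Single week, raw values: variance 2(1 − ρ)σ². With change scores: 4(1 − ρ)σ². Ratio of standard errors = √(4/2) = 1.41.
- Two-week mean, raw values: variance 4 × 0.25 × (1 − ρ)σ² = (1 − ρ)σ². With change scores: (1 + 2)(1 − ρ)σ² = 3(1 − ρ)σ². Ratio = √3 = 1.73.

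The ratios do not depend on ρ. Under this assumption, following the wording of section 2.1 literally with period baselines would lose precision.

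**3. Which week is baseline?** The cues all point to the time just before dosing: Day 1 pre-dose in protocol 3.1, and the post-washout, pre-dose laboratory rule. Set against the design:

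| Interval | Length | Does it contain the 7 days before Day 1? |
|---|---|---|
| Short run-in | Day −7 to −1 | Yes, it is the whole interval |
| Long run-in | Day −14 to −1 | Yes, its second week |
| Shortest washout | 7 days | Yes, it is the whole interval |
| Longest washout | 28 days | Yes, its last week |

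The last seven days before Day 1 are the only seven-day window that every permitted interval contains.

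**4. Carryover check with that week.** Let X1 and X2 be the baseline weeks of Periods 1 and 2, δ the drug effect, and c the fraction of δ still present in X2 for the Drug/Placebo sequence. With one week per period, the treatment factor reduces to two levels, and the treatment term is

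[mean(X1 − X2 | Drug/Placebo) − mean(X1 − X2 | Placebo/Drug)] / 2 = −cδ/2.

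The check can therefore be run and its result interpreted. Protocol 11.4.2 asks only for a similar analysis, which leaves room for the two-level factor. Neither document attaches a decision rule to the result.

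**5. Incomplete diary weeks.** At the entry threshold of 3 stools a day (protocol 4.1), a full week is 3 × 7 = 21. Summing 5 recorded days without adjustment gives 3 × 5 = 15, which is 29% low. A daily mean times 7 gives 15/5 × 7 = 21, and the shortfall disappears. The treatment weeks raise the same question, so it is not specific to baseline.

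**The case for a change.** The strongest case on the other side is that the carryover result depends on the window, and the team choosing it is unblinded. Suppose the drug effect decays with a half-life of 2, 4 or 7 days (assumed; the documents give no offset rate). After a 28-day washout the check would read 0.16, 0.27 or 0.34 of δ if the first seven washout days were used, and 0.00, 0.01 or 0.04 if the last seven were. That spread is arithmetically right, but it requires the week straight after the last Period 1 dose to be called baseline, against both baseline rules in the documents. After a 7-day washout the two windows are the same days and there is nothing to choose.

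A residual effect would also reach the treatment weeks. After a 7-day washout the same half-lives leave on average 0.03, 0.16 or 0.34 of δ in Period 2 Week 1. Only one sequence is affected, so the Week 1 contrast shrinks by half of that: 0.01, 0.08 or 0.17 of δ. This is a matter of washout length, and no definition of the baseline week alters it.

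Some of the objection stands. The window and the day-count rule are not in the readable text. Screening may run to Day −2, so a few patients might have fewer than seven diary days before Period 1. The cancellation in step 1 is exact only for patients with both periods; about 30 are enrolled for 24 completers, so roughly 6 may contribute one. Finally, the body of Table 8-1, protocol 11.5.1 and the table shells cannot be seen, and a rule may be there.

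**Conclusion.** The mismatch in wording is real and the baseline week is unwritten, but neither calls for a change to the plan. The effect on the complete-data drug-placebo contrast is zero, because the model does not use the stool baseline and a common baseline would cancel anyway. Period-specific change scores would raise the standard error 1.41 to 1.73 times under equal correlation; if correlation fades with time, the loss would be smaller.

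The window touches only a carryover check with no consequence attached and descriptive baseline tables, in a trial that both documents call non-confirmatory. An analyst can reasonably take the seven diary days before each Day 1, run the check with one week per period, and count days as in the treatment weeks. Rewording section 2.1 would need a protocol amendment with the approvals listed in protocol 13.1, for no change in any result.

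This rests on the natural reading of baseline being the one used, and on the carryover check staying supportive, as the SAP labels it.

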2.2 Secondary objective(s)

Secondary objective(s)	Endpoints related to secondary objective(s)

• To assess the pharmacokinetics of LJN452 in pBAD patients.• To assess the effect of LJN452 on use of rescue medications during the study period.	
• Tmax, Cmax and AUCtau of LJN452.• Use and type of rescue medications.

Corporate Confidential Information

3 Investigational plan

[figure not shown]
3.1 Study design

This is a multi-center, double blind (patient and investigator blind, sponsor open label), randomized placebo controlled, crossover study to assess safety, tolerability and efficacy of LJN452 in patients with primary bile acid diarrhea (pBAD). In this study approximately 30 patients will be enrolled to have 24 completers.

This is a non-confirmatory trial.

Each patient will undergo a screening period (28 days), run-in period (washing out previous treatment effect) (up to 14 days), 2 treatment periods (14 days each), washout period (at least 7 up to 28 days) between the treatment periods and end of study.

Figure 3-1 Study design schematic

Patients will be assessed for eligibility to enter the study at the screening visit.

Each patient will perform following visits

Screening visit: Day -28 to -2

During the screening period all patients will undergo screening assessment, which may be completed over multiple visits as per the patient's convenience. The screening results will be valid for 28 days, if any patient is beyond the screening validity, the patient can be re-screened. Results for all screening assessment must be available before the baseline/Day 1 pre-dose assessment.

If the eligibility is confirmed patients will be asked to discontinue their sequestrants. Patients will be handed over patient diary to record their daily stool type and frequency using Bristol Stool Chart and use of rescue medication (loperamide intake). The patient diary is expected to be used by patients' throughout the study duration.

Rescue medication will be loperamide only and patients will be instructed to take 2 mg dose only after passage of 4 stools of Bristol Stool Scale Type 6 (Fluffy pieces with ragged edges, a mushy stool) or Type 7 (Watery, no solid pieces, entirely liquid). This dose may be repeated only after 4 hours have elapsed or passage of 4 further stools of Type 6 or 7 (whichever occurs first). A total of no more than 16mg of loperamide may be taken in a 24 hour period. No BA sequestrants should be used by the patients during this study.

Run-in period (Day -7 to -1 or Day -14 to -1)

Patients who have not used bile acid sequestrants for pBAD in the previous week at the time of screening will be evaluated for inclusion/exclusion criteria during the screening visit, and if found eligible will enter a 1 week run in period (Day -7 to -1) prior to the double blind randomized treatment phase.

Eligible patients who are treated with bile acid sequestrants (at least one dose during the previous two weeks) will be asked to stop their medication and enter the 2 weeks run-in period (Day -14 to -1) of the study. Patients will be allowed to take rescue medication (loperamide), which will be recorded as concomitant medication.

Patients will continue to use patient diary to record stool type and frequency along with use of rescue medication.

Results for all screening assessment must be available before the baseline/Day 1 pre-dose assessment. Screening and run-in visits may be combined for logistic reasons.

After the run-in period, patients will enter the double blind randomized treatment phase.

There will not be a separate baseline visit, but pre-dose assessment on Day 1 will be considered as baseline assessment.

Treatment Periods (Day 1-14):

On Day 1, patient will handover stool sample collected before dosing as pre-dose stool sample. Pre-dose PK, PD and biomarker samples will be collected before dosing.

In treatment period 1 on Day 1 patients will receive either 60 µg LJN452 or placebo orally once daily for 14 days in a 1:1 ratio. Pharmacokinetic (PK), pharmacodynamic (PD) and safety samples will be collected on Day 1 for up to 8 hours post dose and on Day 2 pre -dose, which corresponds to 24 h after Day 1 dosing. Some PK and PD sample time points on Day 1 and Day 2 can be optional, see [Assessment Schedule](#).

Patients will be handed over trial medication, to be administered at home enough to cover dosing for 14 days in each period. Throughout the 14 days of the treatment period, patients will be directed to take study drug at home with water in the morning in a fasting state, 2 hours prior to the first meal of the day, preferably at the same time of the day.

Following dosing, patients will return to clinic for PK, PD, BM and safety assessment at various time points as described in the [Assessment Schedule](#).

The patients will return to the clinic for a series of PK, PD and biomarker sample collections on Day 12.

After 2 weeks of treatment with LJN452 or placebo, patients will undergo a washout of at least 7 days, up to a maximum of 28 days. At the end of washout period, patients will return to the study site for period 2 of the study. Period 2 will be identical to period 1 except that the treatments will be crossed over.

Patient diary will be used to capture stool frequency, consistency and rescue medication. Intake of loperamide will be allowed, but will be recorded in the concomitant medication section of the CRF.

Study Completion visit:

The patients will return to the site 7 days' ± 2 days after the last dose to undergo the study completion evaluations. Following completion of all assessments, the patients will be discharged from the study. If for any reason the patient is withdrawn from the study, the patient will return to the site 7 days after the last dose to undergo the study completion evaluations. Following completion of all assessments, the subject will be discharged from the study. Safety assessments will include physical examinations, ECGs, vital signs, standard clinical laboratory evaluations (hematology, blood chemistry, and urinalysis) adverse event and serious adverse event monitoring.

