3.2 Rationale of study design

This randomized, multi-center, double blind (patient and investigator blind, sponsor open label), placebo-controlled, cross-over study is designed to assess safety, tolerability and efficacy of LJN452 at 60 μ g relative to placebo in patients with pBAD, as assessed by a reduction in stool frequency and stool type score after 2 weeks of double-blind treatment.

A cross-over design reduces variability as the treatment comparison can be done within patient.

Randomization will be maintained at 1:1 ratio over the entire study in order to avoid any sequence bias.

Multiple sites will be used to enroll patient in this study due to the underlying prevalence of diagnosed pBAD. It is known that differences in criteria exist in the diagnosis of pBAD in different regions.

In order to maintain the scientific integrity of the study, investigators and patients will remain blinded regarding the allocation of active or placebo. The clinical trial team will be unblinded throughout the dosing phase to allow analysis of safety and PK/PD data.

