6.9 Rescue medication

Use of rescue medication (loperamide) will be allowed and must be recorded on the patient diary/Concomitant medications/Significant non-drug therapies CRF after start of study drug.

Rescue medication will be loperamide only and patients will be instructed to take 2 mg dose only after passage of 3 stools of Bristol Stool Scale Type 6 (fluffy pieces with ragged edges, a mushy stool) or Type 7 (watery, no solid pieces, entirely liquid). This dose may be repeated only after 4 hours have elapsed or passage of 4 further stools of Type 6 or 7 (whichever occurs first). A total of no more than 16 mg of loperamide may be taken in a 24 hour period. No BA sequestrants should be used by the patients during this study.

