11.5 Analysis of secondary and exploratory variables

The number and percentage of subjects using loperamide will be tabulated by treatment. Total weekly loperamide use (in mg) will be summarized by treatment and visit (including baseline). The stool index, calculated as [weekly stool frequency*mean stool form]+loperamide use [weekly mg*3], will also be summarized and analyzed using a linear mixed effects model including sequence, period and treatment as fixed effects and subject nested within sequence as a random effect.

Corporate Confidential Information

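### The protocol gives two different triggers for the first loperamide rescue dose: 4 loose stools in section 3.1 and 3 in section 6.9

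*Protocol*

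**What the plan says.** Protocol section 3.1 (Study design) gives the rescue instruction under the screening visit, together with the handing out of the diary that is used for the rest of the study: "patients will be instructed to take 2 mg dose only after passage of 4 stools of Bristol Stool Scale Type 6" or Type 7. Section 6.9 (Rescue medication) has almost the same paragraph: "patients will be instructed to take 2 mg dose only after passage of 3 stools of Bristol Stool Scale Type 6" or Type 7. The rest agrees. Both sections carry the repeat rule "This dose may be repeated only after 4 hours have elapsed or passage of 4 further stools of Type 6 or 7", whichever comes first. Both cap intake at 16 mg in 24 hours, allow loperamide as the sole rescue agent and bar bile acid sequestrants.

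Rescue use is an endpoint. Section 2.2 lists "Use and type of rescue medications" as secondary. Protocol section 11.5 and SAP section 6.1.3.3 tabulate the number and percentage of loperamide users by treatment, summarise weekly milligrams by treatment and visit with baseline included, and analyse a stool index equal to weekly frequency times mean form plus 3 times weekly loperamide milligrams. The SAP does not restate the trigger.

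A smaller mismatch concerns the agent. Section 8.3.2 (Patient diary) admits loperamide or an equivalent, whereas sections 3.1 and 6.9 admit loperamide alone and the SAP tables count loperamide alone.

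**The concern.** The two instructions cannot both be followed when a patient has passed exactly three Type 6/7 stools: a dose at that point is allowed by section 6.9 and not by section 3.1. Two things follow.

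- **Level of the endpoint.** A lower trigger lets patients dose on more days. Weekly milligrams rise with it, and so does the stool index. In a multi-center trial, sites working from different sections would add between-site variation in both.
- **Compliance.** Section 13 requires significant protocol deviations to be recorded and reported. Whether a dose after the third stool is a deviation at all has no single answer in the current text.

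The primary estimates of stool frequency and form are not part of this concern.

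**Working it through.** The plan has no figure of its own to reproduce here: it gives no distribution of daily loose stools, and the sample size section is redacted. The contradiction rests on the text. The arithmetic only illustrates its size.

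**Text comparison**

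| Element | Section 3.1 | Section 6.9 |
|---|---|---|
| Type 6/7 stools before first 2 mg | 4 | 3 |
| Repeat | 4 h or 4 further stools | same |
| Cap per 24 h | 16 mg | same |
| Agent | loperamide only | same |

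**From the documents.** Each dose is 2 mg and the index weight is 3 per mg, so one dose adds 2 × 3 = 6 index points.

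**Assumptions.** The number X of Type 6/7 stools per day is Poisson with mean m from 2 to 6. Stools are counted by day, since neither section states a counting window. Every permitted dose is taken, and loperamide does not change later stools.

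**First doses only.** The wordings disagree only on days with exactly three such stools, so the gap in triggered days per week is 7 × P(X = 3), with P(X = 3) = e^(−m) m³/6. For m = 3: P = 0.2240; 7 × 0.2240 = 1.568 days; × 2 = 3.14 mg; × 3 = 9.41 points.

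| m | Days/week | mg/week | Index points/week |
|---|---|---|---|
| 2 | 1.263 | 2.53 | 7.58 |
| 3 | 1.568 | 3.14 | 9.41 |
| 4 | 1.368 | 2.74 | 8.21 |
| 5 | 0.983 | 1.97 | 5.90 |
| 6 | 0.625 | 1.25 | 3.75 |

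For scale, if every stool is Type 6/7 and scored 6, the frequency-times-form term is m × 7 × 6 = 84, 126, 168, 210 and 252. The gap is then 9.0%, 7.5%, 4.9%, 2.8% and 1.5% of it.

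**With repeat doses.** Simulation of 200,000 days per mean: stool times uniform over 16 waking hours, each repeat at the earlier of 4 hours or 4 further loose stools, at most 8 doses (16 mg).

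| m | mg/week, 3-stool wording | mg/week, 4-stool wording | Gap, mg | Gap, index points |
|---|---|---|---|---|
| 2 | 8.5 | 3.2 | 5.3 | 15.9 |
| 3 | 16.8 | 8.6 | 8.1 | 24.4 |
| 4 | 24.4 | 15.2 | 9.3 | 27.8 |
| 5 | 30.8 | 21.6 | 9.2 | 27.7 |
| 6 | 36.0 | 27.3 | 8.6 | 25.9 |

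Gaps were computed before rounding; the simulation standard error is at most 0.03 mg. This version doses at 4 hours even when no further loose stool has occurred, so it is close to a ceiling. If a repeat is taken only at a loose stool (the first at or after 4 hours, or the fourth further one), the gap is about 3.2 to 5.8 mg per week, or roughly 10 to 17 points.

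**Percentage of users.** The chance of at least one triggered day in a 14-day period is 1 − (1 − p)^14, where p is the daily trigger probability. Under 3 versus 4 stools it is 99.6% versus 88.5% at m = 2 and 100% versus 99.8% at m = 3, with no visible difference from m = 4 upward.

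**Drug–placebo contrast under one fixed rule.** Suppose the treatments produce means of 5 and 3. From first doses, 14 × (0.875 − 0.577) = 4.2 mg per week under the 3-stool wording and 14 × (0.735 − 0.353) = 5.4 under the 4-stool wording (unrounded probabilities). With repeats, the contrasts are 30.8 − 16.8 = 14.0 and 21.6 − 8.6 = 13.0.

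**The case against.** The best reply is that this is an editorial slip with little statistical consequence. The trial is non-confirmatory and the SAP places the loperamide tables and the index under supportive analysis. The comparison is within patient ("A cross-over design reduces variability as the treatment comparison can be done within patient") and the design states "Period 2 will be identical to period 1 except that the treatments will be crossed over", so a constant instruction largely protects the treatment contrast. The percentage of users barely moves at a mean of 3 or more, and the type of rescue does not depend on a stool count. SAP Table 4-1 lists only missing consent and no study drug received as exclusion codes, so no listed code would remove a patient for rescue timing. The Site Operations Manual, not available here, may carry a single count.

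Most of this stands, and it limits the point to weekly milligrams, the index and the classification of deviations. Three parts need qualifying. Under a constant rule the size of the contrast can still shift modestly, as the last calculation shows, although that is not bias. A bias could arise if a patient's instruction changed between periods. And a single count in the manual would leave the protocol contradicting itself.

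The sections might also be read by phase, since the first sits under screening and the second speaks of recording after study drug starts. Neither limits its count to a phase. On that reading baseline and on-treatment milligrams, which are summarised together, would follow different rules.

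On section 8.3.2, an equivalent might mean another loperamide product, but the text does not say so.

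**Conclusion.** The concern holds. Sections 3.1 and 6.9 give incompatible triggers in current text, and nothing in the protocol or SAP resolves them. The consequence is moderate: the level of weekly loperamide use and of the stool index is undefined by about 1 to 3 mg and 4 to 9 points per week on first doses alone, rising to about 5 to 9 mg and 16 to 28 points if every permitted repeat is taken. These sizes rest on the assumed Poisson means and full use of permitted doses; actual use could be lower. The contradiction does not rest on them. The primary analysis is not shown to be harmed, and which wording reached patients is unknown. This should be fixed; confidence in the contradiction is high.

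**What to change.** Reconcile protocol sections 3.1, 6.9 and 8.3.2 so that one first-dose trigger and one statement of permitted rescue agents appear throughout, and check that the diary instructions and the Site Operations Manual match. The choice of count and agent belongs to the sponsor's clinical lead; this review takes no position on it. If patients have already been instructed, record which wording each site used and confirm that it was the same for each patient in both periods.

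The cost is a short written amendment with the approvals in protocol section 13.1 (sponsor, IRB/IEC, and Health Authorities where required), the document check and, where needed, the record of wording. No extra patients or procedures are needed.
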